Measurement of IL6. Using techniques such as ELISA and fluorescence resonance energy transfer (FRET) assay methodology, the levels of active IL6 will be calculated and reported.

Methods for Data Collection & Data Management

Variable	Significance	Sampling time	Source	Specific Aim
Age	Demographic	Baseline	EHR	n/a
ABI	Exclusion criterion	Baseline - enrollment	ABI done after ICF	n/a
% nonviable wound tissue	Appearance of wound bed	Baseline Day 0 and Day 8	Provider assessment	Aim 1
Quantitative Cultures (planktonic and biofilm)	Microbial identification	Day 0 (pre-test), + Day 4 and Day 8	Wound samples	Aim 1
Wound Size in cm ² (volume: L x W x D)	Descriptive	Baseline Day 0 and Day 8	Wound measurements	Aim 2
Interleukin 6	Marker of inflammation	Day 0 (pre-test), + Day 4 and Day 8	Wound sample (fluid and/or tissue)	Aim 2
Matrix metalloproteinases (MMP-2 and 9 equivalent)	Elevated MMPs associated with non-healing wounds	Day 0 (pre-test), + Day 4 and Day 8	Wound sample (fluid and/or tissue)	Aim 2
Perceptions of therapy	Perceptions of debridement	Day 0 (pre-test) + Day 8	Patient, Caregiver & Clinician Surveys	Aim 3

Survey Methods

Subjects will be asked to complete a paper survey at Day 0, Day 4 and Day 8 of the study, querying the patient's perceptions of: wound pain, satisfaction with most recent/current wound care method, ease of

care, effectiveness of most recent wound treatment, aesthetics of current wound treatment and toward sharp debridement and maggots for wound care.

Caregivers and wound clinical providers will be asked to complete a paper survey at Day 0 and Day 8 of the study (if wound clinician is caring for more than one study subject, they will be asked to complete a survey at day 0 of first subject, day 8 of first subject and 3 months later or at completion of the study for each type of debridement), querying them about their perceptions of what the patient's experience was regarding the most recent wound debridement methods as well as satisfaction with most recent/current wound care method, ease of care, effectiveness of most recent wound treatment, aesthetics of most current wound treatment and toward sharp debridement and maggots for wound care.

Data Analysis

Data will be summarized with descriptive statistics. Data will be checked for implausible values, missingness, and distributional form. Data transformations will be made as necessary to achieve normality. To address Specific Aim 1 (comparing the clinical effectiveness of a self-contained larval debridement therapy with a bedside sharp debridement therapy), the numeric outcome measures of changes (post minus pre) in percent of non-viable tissue and bacterial biofilm will be analyzed using independent samples t-tests. To address Specific Aim 2 (comparing wound characteristics of larval debridement and bedside sharp debridement therapies) over time, longitudinal generalized mixed models (GLMMs) will be used with the dependent repeated measures being wound characteristics (e.g., inflammatory markers, wound size) and the independent variable of group assignment (larval versus sharp debridement). To address Specific Aim 3 (investigating patient, caregiver, and clinician perceptions of larval therapy dressings and bedside sharp debridement using self-reported assessments, independent samples t-tests will be used to analyze data measured at the interval level, Wilcoxon rank sum tests will be used to analyze data measured at the ordinal level, and chi-square tests (or Fisher exact tests in the case of data sparseness) will be used to analyze categorical data. All hypotheses testing will be two-sided using a level of significance of .05. Data will be analyzed as "intent to treat." SAS version 9.2 (Cary, N.C.) will be used for all analysis.

Data and Safety Monitoring Plan

The main study PI will review the collected data monthly during sample collection to identify any possible breach of the study protocol, including incorrect consent procedure or data storage. This study will be monitored by the University of Florida IRB and the NF/SG VHS R&D Committee as well as the Research Compliance Officer, who have institutional responsibility to oversee the progress of research studies and the safety of study participants. The PI has the responsibility to promptly report any adverse event or breach of the study protocol. Should any adverse event or breach of protocol occur, they will be reported in accordance with the IRB standard operating procedures enforced by the IRBs at University of Florida, North Florida Regional Medical center, and the NF/SG VHS research Offices. All of the research team members will be required to pass the mandatory training programs for human subject research and be certified by the IRB for conducting this study.

Inclusion of women, minorities and/or children: Efforts will be made to recruit women and minority patients.

7. Possible Discomforts and Risks:

Adequacy of Protection from Risk

Potential Risks: The risks to human subjects associated with this study are minimal related to the collection of wound samples, since these samples will be collected by the PI or patient's wound care clinicians. The risks related to the debridement techniques are also minimal since bedside sharp debridement is typically a standard of care in these patients with lower extremity or diabetic foot ulcers and the risk of larval debridement therapy is considered to be less than that of sharp debridement. Potential risks related to sharp debridement, and to a lesser extent, to larval debridement, may include: bleeding, pain, increased wound draining, infection, increased wound odor, and in the case of larval

debridement, a “crawling” sensation in wound. Potential risks related to subject, caregiver and wound clinician participation with the study survey component are minimal, due to the fact that no sensitive information is being collected.

Prior to study, it will be approved by the VA Subcommittee on Clinical Investigation (Research and Development committee) and the University of Florida Health Science Center Institutional Review Board (UF IRB). The UF IRB is the official review and approval process for all VA research studies at NF/SG VHS, and is the IRB of record for the additional North Florida Regional Medical Center Site. Despite the low risk of this study, we will take measures to safeguard all of the study participants (including caregiver and clinician) from inconvenience, unnecessary discomfort and Personal Health Information risk. First, we will meet with patient, caregiver and clinician at a convenient time for the participant, caregiver, and wound care provider/clinician. The surveys will be brief and will not ask for personally identifying or sensitive information (see Appendixes). We will take measures to safeguard any data collected and keep all data collected in a secure locked file on the VA server and in locked file cabinet (copies of regulatory documents and ICFs pertinent to NFRMC will be kept on site at NFRMC by site PI, [name]). We will ensure that the participants are fully informed about the procedures, risks and objectives of the wound sample collection. The informed consents and all data collected at the clinician’s office or secondary study site(s) will be transported in a locked file box by the research team member and then stored in the Research office in a locked file cabinet. For VA participants, the original is scanned into patient’s electronic health record/CPRS per VA regulatory protocol; for NFRMC participants, the original is copied and kept onsite at NFRMC in a locked file cabinet with the study binder.

Potential Financial Risks: There are no anticipated financial risks to study subjects. The larval BioBags and lab tests performed on the wound samples collected from human participants for the sole purpose of this study will be the responsibility of the principal investigator.

8. **Possible Benefits:**

Benefits to Subjects

Potential Health Benefits: The human subjects in both arms of this study may benefit from the debridement therapies, as this has been demonstrated to improve wound healing trajectories. Information gained from this research may benefit future patients who suffer from chronic wounds.

9. **Conflict of Interest:**

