The primary purpose of this study is to assess the efficacy of larval debridement therapy (LDT) with bagged, sterilized, live, medicinal blow fly (*Lucilia sericata*) larvae (or "BioBags") versus bedside sharp debridement in removing harmful bacteria, biofilm and necrotic tissue from chronic wounds to promote wound healing. Characteristics associated with chronic wound environments will be evaluated through analysis of samples of tissue taken from wound beds before and after both types of debridement. One hundred and forty patients \geq 21 years of age with an open, full thickness wound which is healing by secondary intention (of greater than 8 weeks duration and requires debridement) will be invited to participate. This recruitment number accounts for estimated 10% attrition rate, so final sample number is anticipated to be 128 subjects (64 in each arm). Samples of wound bed tissue and slough tissue (if present) will be collected on Days 0, 4 and 8 or prior to and after each larval debridement intervention or sharp debridement (control). Photos will be taken of the wound bed on Days 0, 4 and 8 or just prior to and after each debridement method. A randomized sampling procedure will place individuals into one of two groups: The intervention group will receive larval debridement therapy once every 4 days for 2 applications (with saline moistened gauze as cover dressing changed daily) and the control group will receive sharp debridement therapy every 7 days for 2 debridements (with wound gel dressing changed daily).

The wound and wound environment will be characterized by assessing wound Matrix Metalloproteinases (MMPs), inflammatory cytokines and the presence of total bacteria, planktonic (free floating) bacteria, and biofilm (sessile) bacteria. Clinicians will be asked to grade the amount of non-viable tissue apparent in the wound bed, appearance of any signs of infection and overall visual appearance of the wound at each visit. Wound size will also be assessed. Subjects will be asked to rate their wound related pain level at each visit before and after the debridement method is applied. Subjects, caregivers and clinicians will be asked to complete a short survey to self-report their perceptions of each method of debridement. Data will be analyzed using bivariate and multivariate methods.

4. **Background:**

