Chronic wounds are a significant health problem in the U.S.. Chronic wounds are defined as wounds that have "have failed to proceed through an orderly and timely reparative process to produce anatomic and functional integrity." Health care costs related to the management and treatment of chronic wounds in the U.S. exceeds \$20 billion annually. For many health care providers, the treatment and management of non-healing wounds is challenging. Traditionally, basic wound care has consisted of surgical debridement, manual irrigation, moisture retentive dressings, and topical and/or systemic antimicrobial therapy. Although there has been tremendous progress in the science of

wound healing, the prevalence and incidence of chronic wounds and their associated complications continues to escalate.

The presence and complexity of bacterial biofilms in chronic wounds has recently been recognized as a key aspect of non-healing wounds. Bacterial biofilms are sessile colonies of polymicrobial organisms (bacterial, fungal, and possibly, viral) which are often symbiotic. These biofilm colonies produce a protective coating to protect the colonies from host defenses. The character of this protective substance which is unique to biofilms is dynamic and production of its components seems to be triggered by hostile environments in the wound bed (such as the presence of topical antibiotics). Biofilms have been shown to have survival and defense mechanisms that: 1) inhibit the healing aspects of inflammatory cells; 2) resist antibiotics (topical and systemic) and other therapies; and 3) initiate cell to cell communication pathways (quorum sensing) which facilitate new biofilm growth, resulting in recalcitrant non-healing wounds.

Wound larval debridement therapy (LDT) has been shown to have promise in healing chronic wounds by eradicating biofilms. Recently (2012), the PI was part of a team of investigators who collaborated with the University of Florida Wound Research Laboratory and conducted several in vitro experiments to demonstrate the efficacy of larval exposure to biofilm (Cowan et al., 2013). These studies demonstrated bacterial biofilm (*Pseudomonas aeruginosa* (PA01) bacteria and *Staphylococcus aureus* (SA35556) bacteria) grown on pigskin explants were completely eradicated within 48 hours of exposure to loose medicinal maggots from Monarch Labs (larvae).

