information). The clinicians will also be asked to make a Recruitment Brochure available to potentially eligible patients (those with lower extremity or diabetic foot ulcers over 8 weeks duration). In addition, study flyers will be sent to select VA wound and podiatry offices in the NF/SG VHS. Providers will be asked to contact study team if any patient is willing to hear about the study. If the patient is willing to hear about the study, they may contact a study team member from the contact number on the recruitment brochure or the provider can let the patient know when the research team member is scheduled to be in the provider clinic office and the patient may talk directly to the research study team member for more information. If patients call a research team member, they will have their questions answered but will not be screened over the phone. They will be scheduled to come into the provider office to discuss the study with a research team member and review informed consent. Members of the research study team will review the informed consent with the patient and enroll the subject if they agree to participate. Wound clinicians will not be asked to consent subjects, or to provide a list of patients or appointment times to research team. However, the subject's wound providers (clinicians) will be the ones to perform the sample collection and apply the LDT or bedside sharp debridement. The sample also includes one available caregiver of the patient (non-professional) to answer the caregiver surveys if willing, and the wound care providers, who will be asked to answer the clinician survey regarding perceptions of debridement methods.

Sample Size Power Analysis: Power analysis is based on the patient sample and the primary study aim of comparing debridement methods on clinical effectiveness. The POWER procedure in SAS version 9.2 (Cary, N.C.) was used to conduct the power analysis. Assuming a Type I error rate of .05 and two-sided testing, a sample of 64 is needed in each group to detect a medium effect size of .50 with at least 80% power. This magnitude of effect is considered clinically significant.

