Patient characteristics to be recorded: Age (in years), gender (Male/Female), presence of diabetes diagnosis (any "no" would be excluded from study), smoking behavior (Yes/No), presence or absence of pedal pulses (Yes/No) and Ankle Brachial Index (ABI), relevant laboratory values, culture reports and other pertinent medical history (co-morbid conditions). Additionally, telephone numbers will be obtained, with the participants consent, in order to call and remind the participant the day before there next upcoming visit.

Inclusion criteria: (1) Veterans over 21 years of age; (2) with chronic lower extremity or diabetic foot ulcers (wound duration over 8 weeks); (3) who at the clinician's judgment requires wound debridement (25% or more of wound bed covered with non-viable tissue); (4) wound size 1.5 cm (roughly the size of a quarter) or larger in diameter.

Exclusion criteria: (1) Cognitive impairment that would interfere with patient signing own Informed Consent; (2) Veterans on active anticoagulant therapy with most recent (within last week) PT/INR (international normalized ratio of prothrombin time) > 3.0, or other significant bleeding risk; (3) Active immune suppression just prior to or during study (on systemic corticosteroids* within 7 days prior, or chemotherapy for cancer or RA treatment within 4 weeks prior to study, or with diagnosis of HIV/AIDS) - *Nasal steroid sprays will not be excluded; (4) Active systemic antibiotics is an exclusion; (5) Absent dorsalis pedis pulses and Ankle Brachial Index (ABI) < 0.5 is an exclusion (indicates critical limb ischemia). Other possible reasons participants could be removed from this study include: transfers to other non-VA facilities, participant is unable to tolerate tissue sampling even with local anesthesia, at the discretion of the provider for clinical reasons, and/or inability to comply with scheduled research visits. Furthermore, if the participant has significant wound healing so that sampling is not possible after the initial sampling, they will be removed from the study.

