Human Subjects Involvement and Characteristics: One hundred and forty consented veterans and their (non-professional) caregivers will be randomly assigned to one of two study arms: (1) Larval Debridement Therapy (LDT) or (2) Bedside Sharp Debridement (control). The intervention group, or LDT participants, will undergo LDT every 4 days for 2 applications as the main method of debridement strategy. They will have wound samples collected before the initial larvae are applied after 4 days of larval therapy and after 8 days of larval therapy. They will also both be asked to complete a short paper

survey on Days 0, 4 and 8. The subject's wound clinician will also be asked to complete a similar survey (only one round of surveys per consented wound clinician) at Day 0 and Day 8 and 3 months later or at completion of study regarding perceptions of wound debridement therapy.

The control group (bedside sharp debridement) will receive sharp debridement of their wounds 7 days apart x 2 sharp debridements and also have wound samples collected before the initial sharp debridement (Day 0), 4 days after the initial sharp debridement (Day 4), then eight days after initial sharp debridement, which will be 24 hours after the second sharp debridement (Day 8).

Both groups will also receive standard care and therapies ordered by their VA health care providers for their chronic wound care (excluding systemic antibiotics and topical wound antimicrobials), and standard emergency contact numbers. The study duration for the participants is 8 days,

IRB, Safety Committee, Information Security Officer (ISO) and VA R&D committee approval will be obtained prior to beginning this research study. The sample size is anticipated to be 140 total subjects (desired $n=128 + 10\%$ attrition). The desired sample size for data analysis is 128 to achieve adequate sample size for statistical power.

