X post-measure (**sample 2**); Pain survey; photos
Apply larvae bag 2
- Day 8 - **X** final measures (**sample 3**); surveys; photos

SD group

- Day 0 - **X** pre-measures (**sample 1**); surveys; photos
Sharp Debridement 1
- Day 4 - **X** post measures (**sample 2**); pain survey; Wound photos
- Day 7 - Sharp debridement 2 & photos
- Day 8 - **X** final measures (**sample 3**); surveys; photos

Data Collection & Data Management

Measurement of bacterial colonization. A microbiological assessment of the wound samples will be performed. Samples will be measured for both planktonic (single) bacteria and biofilm bacteria by standard clinical microbiology techniques with serial dilution and plating on complete agar medium

plates. Colony forming units (CFUs) will be measured after approximately 24 hours of culture under standard laboratory conditions. Levels of planktonic bacteria and biofilm bacteria will be compared within each sample and chronologically within each patient. Photos will be reviewed by blinded wound clinicians and rated on amount of necrotic tissue present visually in wound bed at each sampling time (reported on scale 0 – 10 based on 0%, 1 = 10% or less, etc.). Data collected from human subject's electronic health record will include characteristics such as wound etiology, wound location/duration, wound treatments, wound photos, wound progress notes, age, gender, comorbid conditions, pertinent laboratory values and medical history. This data will be conducted only by trained research team members designated in the IRB approved study protocol over the duration of the study.

Only de-identified pertinent information per subject sample such as age of subject, visit number (Day 0, 4, 8), location of wound, duration of wound, co-morbid conditions, medications and current wound treatments will be shared with the investigational laboratories or their personnel. Only the PI, site PI, Co-Investigators, and study coordinator(s) will have access to the subject PHI and study folders. UF lab has agreed to destroy any remaining samples at the conclusion of the current study.

Measurement of MMPs. Using techniques such as ELISA or fluorescence resonance energy transfer (FRET) assay methodology, the levels of active MMPs (or measures of MMP activity) will be calculated and expressed as pg/ml of wound fluid and pg/mg protein.

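### The Aim 1 biofilm analysis has no term for antimicrobial use before Day 0, which the entry criteria leave open but on-study care excludes; the possible cost is precision, not bias

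*Combined protocol and SAP*

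**What the plan says.** All references are to the combined protocol and SAP.

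- **Entry (section 6, Exclusion criteria, both sites).** The fourth item reads "4) Active systemic antibiotics is an exclusion". It gives no look-back. The item before it does: 7 days for systemic corticosteroids, and 4 weeks for chemotherapy or RA treatment. Topical antimicrobials appear in neither site's list.
- **On study (section 6, Human Subjects Involvement and Characteristics, both sites).** Both arms receive the standard care ordered by their providers, "excluding systemic antibiotics and topical wound antimicrobials".
- **Before the Day 0 sample (Study procedures).** Only an optional saline rinse and blotting is described. There is no washout.
- **Usual care (section 4, Background).** Traditional wound care is said to include "moisture retentive dressings, and topical and/or systemic antimicrobial therapy".
- **Analysis (Data Analysis).** Biofilm CFU is one of two Aim 1 outcomes. Its post-minus-pre change is compared by an independent-samples t-test. No covariate is named.
- **Data collected (Data Collection & Data Management).** Wound treatments are taken from the health record, and the items listed for each sample include "co-morbid conditions, medications and current wound treatments will be shared with the investigational laboratories or their personnel".

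**The concern.** The on-study rule keeps antimicrobials out of the later cultures, but nothing does the same for the Day 0 culture. Background makes prior use plausible in wounds open for more than 8 weeks. If prior use alters the Day 0 count, the change score of a recent user contains a component due to stopping the agent as well as the effect of debridement, while a non-user's does not. In an unadjusted t-test that component goes into the residual variance.

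At stake is the precision of the between-arm comparison of biofilm CFU. Percent non-viable tissue, the other Aim 1 outcome, is not directly affected.

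**Working it through.** **Inputs from the plan** (Sample Size Power Analysis and opening summary). Alpha is 0.05 and tests are two-sided. The requirement is put as "a sample of 64 is needed in each group to detect a medium effect size of .50 with at least 80% power", which makes 2 × 64 = 128 analysed. The effect is given only in standardised form, as a "medium effect size of .50", with no SD for any outcome. I therefore set the SD of the change to 1.

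**Step 1: the plan's own figure.** A two-sample t-test (noncentral t) with d = 0.50, 64 per arm and two-sided alpha 0.05 has 80.15% power. The stated 64 per arm reproduces.

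**Step 2: assumed model.** Let a share *p* of participants be recent users, and let their change be shifted by *r* SD, equally in both arms and independently of other variation. Then:

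- variance factor V = 1 + p(1 − p)r²
- effective effect size d′ = 0.50 / √V

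The documents give neither p nor r. Both are assumptions.

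**Step 3: illustration at p = 0.40**, so p(1 − p) = 0.24, with 64 per arm:

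| r (SD) | V | d′ | Power | n per arm for 80% |
|---|---|---|---|---|
| 0.25 | 1 + 0.24 × 0.0625 = 1.015 | 0.496 | 79.6% | 65 |
| 0.5 | 1 + 0.24 × 0.25 = 1.06 | 0.486 | 77.8% | 68 |
| 1 | 1 + 0.24 × 1 = 1.24 | 0.449 | 71.2% | 79 |

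**Step 4: range over p.** For p from 0.10 to 0.50, power runs from 79.3% to 77.7% at r = 0.5 and from 76.7% to 70.9% at r = 1. The extreme combination p = 0.50 and r = 2 gives V = 2.00 and 51.0%. With a constant shift, V = 1 if nobody or everybody is a recent user.

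**Step 5: bias check.** In 20,000 simulated trials per setting with an equal shift in both arms (p and r of 0.5 and 1, 0.5 and 2, 0.25 and 2), type I error was 0.050 to 0.053 and the mean arm difference was about 0.

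**Step 6: restricting to non-users.** At p = 0.40, about 0.60 × 64 = 38 per arm remain. Power at d = 0.50 is then about 58%.

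**Step 7: cost of adjusting.** The t-test has 126 degrees of freedom. Baseline CFU takes one and the indicator one or two, leaving 124 or 123. If the covariates explained nothing, that loss of degrees of freedom alone would leave power at 80.1%; chance imbalance in the covariates could lower it slightly further.

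**The case against.** Four points on the other side carry weight.

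1. **The mechanism is not documented.** No section reports that prior antimicrobials suppress biofilm counts or that counts rebound when they stop. Background says that biofilms resist topical and systemic antibiotics, which suggests a small shift. It also says that topical antibiotics seem to trigger the biofilm's protective substance, so even the direction is open. Any shift must also survive the debridement given before the Day 8 sample. This stands: the shift is hypothetical.
2. **The power loss is conditional.** With no SD stated, the planning SD may already contain variation from prior use. In that case nothing is lost against plan. This stands too, although adjustment could still gain precision.
3. **Randomisation protects the comparison.** A reader might infer that the arm difference is biased. The documents do not support that: with an equal shift in both arms the expected bias is zero. Nor is chance imbalance in prior use a second harm, since it is the same added variance seen from another side.
4. **The scope is limited.** Topical use up to Day 0 is left open by silence, not expressly permitted. The mismatch in conditions applies only to recent users, whose share is unknown, and active systemic users are already excluded.

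None of this removes the gap in the text or the case for a baseline covariate. The covariate estimates the average shift whatever its sign.

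**Conclusion.** The point holds as a modest one about precision. The entry criteria and the on-study rule treat antimicrobials differently, no washout separates them, and the Aim 1 CFU test has no term for prior use.

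The size cannot be fixed from the documents. With 40% prior use, an additive shift equal in both arms and a planning SD that excludes this variation, power is about 78% for a 0.5 SD shift and about 71% for a 1 SD shift, against 80% planned. These figures are illustrations. A reader might take them, or the 51% extreme, to mean that the trial is underpowered as designed; without a stated SD, prior-use rate or shift, that does not follow. Nor can it be said that Day 0 counts are in fact suppressed.

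**What to change.** 1. Before allocation, code antimicrobial use up to Day 0 as none, topical or recent systemic, from the wound-treatment and medication data already collected. The investigators should define 'recent' in advance.
2. Replace the t-test for the CFU outcome with a pre-specified linear model of log10 CFU change on arm, baseline log10 CFU and this indicator. Baseline CFU belongs in the model because it is planned for every participant and would directly reflect any effect of prior use on Day 0.
3. Label any analysis restricted to participants without recent use as supportive, given its power of about 58% at 40% prior use.

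The cost is one coded field and 2 to 3 degrees of freedom. The documents do not say that stop dates are recorded, so the systemic category may be incomplete for some participants. The model should be fixed before outcome data are seen by arm, because adjustment chosen afterwards is less credible. No change to care or eligibility is proposed.
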